Over 70% of adults in the United States have overweight or obesity (CDC, 2017), which is causally linked to the development and progression of multiple adverse health outcomes (Allison et al., 2008). Weight loss interventions using lifestyle strategies or pharmacotherapy produce clinically meaningful reductions in body mass (Expert Panel, 2014; Magkos et al., 2016). However, due to complex physiological, neuronal and reward-related behavioral process that seek to restore homeostasis (Allison et al., 2008; CDC, 2017; White, Whisenhunt, Williamson, Greenway, & Netemeyer, 2002), maintaining weight loss is challenging and weight regain is common (Hill, Peters, & Wyatt, 2009; Maclean, Bergouignan, Cornier, & Jackman, 2011; MacLean et al., 2015). Due to the high likelihood of weight regain, identification of effective strategies to promote weight maintenance following intentional weight loss is a high priority in the obesity field. Furthermore, it is crucial that interventions be cost-effective and feasibly integrated into existing health-care systems in order to have a broad impact on the long-term health of US adults. Mindfulness-based interventions are novel approaches that could be well suited for weight loss maintenance due to their success in treating other chronic conditions and behaviors with high relapse susceptibility, such as depression and drug/alcohol addiction (Goldberg et al., 2018). Recently, [name] (Co-I) demonstrated that his previously developed Mindfulness-Oriented Recovery Enhancement (MORE) intervention (E. Garland, 2013), which has been shown in multiple NIH-funded randomized clinical trials to significantly reduce a range of addictive habits, is effective at reducing maladaptive eating behaviors in adults with obesity (Thomas et al., 2019). MORE is unique from other existing mindfulness based interventions as it combines traditional mindfulness training with cognitive reappraisal and savoring strategies to promote adaptive reward system function. Due to its comprehensive approach and demonstrated therapeutic effects on physiological, neuronal and reward-related mechanisms linked with appetitive behaviors, MORE may be an effective intervention for preventing weight regain. Preliminary data from an ongoing trial in my laboratory with an 8-week mindfulness-based intervention ([name] & Cornier, unpublished data) indicates that weight regain is minimal (-0.04±1.2% of body weight) and that participants (n=7) report high satisfaction (average scores >9 out of 10 for content and weight-loss maintenance) with the intervention. However, to date, no randomized trial has evaluated the efficacy of MORE for preventing weight regain, nor have the long-term effects of mindfulness-based interventions on weight loss maintenance been investigated.

Purpose and Objectives

The overall objective of this study is to evaluate the effectiveness of a mindfulness-based intervention to prevent weight regain in weight-reduced adults.

A secondary objective is to perform preliminary efficacy testing comparing the impact of MORE vs standard weight loss maintenance advice (CON) on weight loss maintenance and eating-related behaviors (disinhibition, hedonic hunger, food cravings, and ad libitum energy intake).

To meet these objectives, we propose the following aims:

Specific Aim 1: Determine the effect of MORE on weight loss maintenance.

Hypothesis: MORE will result in less weight regain compared to CON after the 8-week intervention, and benefits will be sustained in a 6-month follow-up.

Specific Aim 2: Determine the effect of MORE on reward-related behavioral processes (e.g., food cravings) and ad libitum energy intake.

Hypothesis: MORE group will demonstrate changes in eating behaviors and energy intake associated with preventing weight regain compared to CON immediately after MORE and after 6-months of follow-up.

Study Population

Age of Participants: 18-65

Sample Size:

At Utah:

All Centers: 100

Inclusion Criteria:

We will enroll the following three subgroups (ages 18-65 years):

- Lifestyle weight loss: weight loss of 7% body mass via intentional weight loss within past 6 months; BMI $>25 \text{ kg/m}^2$ prior to intentional weight loss.
- Medical weight loss patients: patients of the bariatric weight loss clinic, weight loss of 7% body mass via intentional weight loss within past 6 months; BMI $>25 \text{ kg/m}^2$ prior to intentional weight loss; stable for 3 months on medications.
- Bariatric Surgery patients: 12-20 months post-operation.

Exclusion Criteria:

Exclusion Criteria: uncontrolled cardiovascular, metabolic, renal, or pulmonary disease; cancer treatment in past 5 years; untreated thyroid disease or other medical condition affecting weight or energy metabolism; severe food allergies; women who are pregnant, lactating, or planning pregnancy during participation in the trial; active psychiatric issues. Scheduled bariatric surgery within the next 6 months. No access to WiFi at residence. No access to a smart device as a personal device (with access to applications). Complete hearing loss.

Additional criteria specific to patients with a history of bariatric surgery: <12 months post-op; weight regain of >5% of body mass post-operation; history of admittance to rehabilitation facility; history of post-op complications that require recent inpatient management; patients who were required to stay in the hospital >1 week post-op; revision surgery patients; heart failure patients.

Additional criteria specific to lifestyle and medical weight loss participants: Bariatric surgery within the past 2 years

Design

Randomized Trial

Study Procedures

Recruitment/Participant Identification Process:

- Chart Review
 - Participants will be recruited from the Electronic Health Record (EHR) in the UU Health system. Participants meeting initial criteria will be contacted via email or opt-out letter, inviting them to complete a medical history screening survey over the phone with a member of the research team to further determine eligibility. We will also recruit via passive techniques (i.e. fliers in campus, clinics, and community locations; newspaper and social media ads).
- Referral
 - Physicians at University of Utah Health primary care clinics will be able to refer eligible patients from their clinical practice to the study. Clinics will either be provided with a simple referral form that patients can complete if interested.
 - Surgeons at The Bariatric Surgery clinic at University of Utah will also refer patients to this study. A Study coordinator will be in clinic to provide study information and enroll referred patients who may be interested in participating.
- Flyers
 - Flyers will be placed on campus and in community centers. Flyers will also be sent out electronically via University of Utah email lists. Advertisement flyers will also be posted on relevant University of Utah research-related websites.
- Follow-Up
 - PI or research assistant will follow up via phone or email (using the [contact] account) once an individual has expressed interest in the study from one of the recruitment techniques. No more than 3 contact attempts will be made.

Informed Consent:

Description of location(s) where consent will be obtained:

Consent will be obtained in: - a private room in the HPR complex - a private room in the Bariatric Surgery Clinic - over a private HIPPA compliant Zoom session (e-consent)

Description of the consent process(es), including the timing of consent:

Informed Consent will be completed in person, or over a private HIPAA compliant Zoom call, with a member of the study team and the potential participant. During the explanation of the consent form and after the study team member goes over the details of the Informed Consent document, the potential participant will be given a chance to ask questions regarding study procedures. The study team member will assess understanding of the consent form and study procedures by asking the potential participant to briefly recite back study-related commitments and procedures. Potential participants will be told that they are free to take the consent form home with them and decide to sign it and participate in the study at a later time if they are uncomfortable with consenting to the study during this visit. In addition, to provide participants with greater time between seeing the consent form and signing it, the consent form will be emailed to participants, and available to them via REDcap, prior to the screening visit so that they can view it on their own time 1-year follow-up visit addition to study: As of March 2023, participant enrollment will be over. At that time, participants who are still in

ongoing data collection (have not completed the six month follow up visit), will be contacted and asked to sign a new consent document ("Informed Consent Document_v.03.13.23_Clean") that outlines one additional contact event at 1 year (6 months following the 6 month study visit). At this time, participants who have formally completed their data collection (have completed the six-month follow-up visit), will be contacted via email (2 contact attempts) and phone (1 contact attempt; for a total of 3 contact attempts) and will be asked if they have interest in enrolling in the study for the 1 year follow up contact event. These participants will be provided a copy of the consent document they previously signed, and they will be provided a new consent document outlining this additional study event (One Year Follow-up Informed Consent Document_v.03.13.23_Clean). If they would like to participate in the 1 year follow up they will be asked to sign the new consent document. These specific changes are being done so that participants who are currently enrolled in the study can simply sign an updated consent document to participate in the 1 year follow up event. And participants who are no longer in contract with the original informed consent document can opt-in to this new study event with a simplified consent document. All processes followed in obtaining the initial consent that are explained above will be followed.

Procedures:

PRE-SCREENING: Subjects who are interested in participating will undergo a pre-screening in which they will answer questions over Redcap, or via a phone screening with trained study staff, about their medical history and they will be assessed on all inclusion and exclusion criteria.

SCREENING: After pre-screening, interested participants that remain eligible will be scheduled for a Zoom screening visit to determine eligibility. After providing written informed consent, participants of childbearing potential will perform a pregnancy test that will be delivered to their home. Upon completion of a pregnancy test participants will be asked to report the results over Zoom. Participants will also be asked to remotely complete the EATS-26 questionnaire (Garner, Olmsted, Bohr, & Garfinkel, 1982) to screen for eating disorder risk, The Patient Health Questionnaire 9-Item (PHQ-9) (Kroenke, Spitzer, & Williams, 2001) to screen for depression, and the Alcohol Use Disorders Identification Test (AUDIT) (Daeppen, Yersin, Landry, Pécoud, & Decrey, 2000) to screen for alcohol use disorders via REDcap. Participants that remain eligible and are willing to participate in the trial will complete the following assessments:

BASELINE TESTING:

- **Body Mass, Height, and Composition** via digital scale, stadiometer, and BodPod (air displacement plethysmography)
- **Validated Eating-Related Behavioral Questionnaires** to assess dietary restraint, disinhibition and hunger (Three Factor Eating Questionnaire); diet-specific self-efficacy (Weight Efficacy Lifestyle Questionnaire); and food cravings (Food Craving Inventory; FCI); Interoceptive Awareness (Multidimensional Assessment of Interoceptive Awareness; MAIA); and savoring (Ways of Savoring Checklist)
- **Free-living Energy Intake (EI)** via automated 24-hr dietary recall (ASA-24) administered online through the Clinical Services Core of the CCTS. This recall will be administered on 3 non-consecutive days, including 2 weekdays and 1 weekend day.
- **Meal Test:** Participants will also complete a baseline meal test visit for assessment of appetite-related markers. Participants will be asked to keep a 1-day food log the day before this testing visit at baseline and asked to repeat this same meal pattern the day before the post-intervention testing visit. Participants will present to the Human Performance Laboratory in the morning after an overnight fast and having refrained from exercise for the prior 48-hours. Participants will next consume a standard breakfast meal (25% of the total energy needs). Repeat appetite evaluations will be performed at 30, 60, 90, 120, 150, and 180 minutes post-meal. Participants will then be offered a buffet-style lunch to measure *ad libitum* energy intake

- **Randomization:** Following enrollment and completion of baseline testing a randomization assignment will be generated by computer and block randomization will be performed within strata defined by sex. Participants will be randomized 1:1 to MORE or CON

INTERVENTION:

Group-Based Interventions

- **MORE:** Participants randomized to MORE will complete the previously developed 8-week, MORE program (E. Garland, 2013). MORE is delivered in a group format, consisting of 8 weekly HIPPA compliant virtual zoom 2-hour sessions. The MORE curriculum will be adapted for this intervention to address food intake behaviors and will provide training in mindfulness techniques to increase awareness of, and self-control over, cravings; reappraisal skills to promote emotion regulation and restructure motivations for highly palatable food intake; and savoring pleasant events and emotions to overcome defects in natural reward processing. In addition to class sessions, participants will complete daily, 15-minute, audio-guided mindfulness, reappraisal, and savoring sessions at home. The intervention will be delivered by a study team member who will receive training and supervision from [name]. Treatment fidelity will be monitored as in ongoing RCTs of MORE (E. L. Garland, Manusov, et al., 2014).
- **CON:** Participants randomized to the control intervention will complete an 8-week healthful lifestyle program via HIPPA compliant zoom sessions. The curriculum will be based on the Diabetes Prevention Program's Prevent T2 for Life program, which is an evidence-based national healthful lifestyle maintenance intervention. This program includes training in healthful eating, meal planning, and recipe modification; time and stress management; adapting lifestyle habits for continued success during holidays, vacations, and other special situations; and relapse prevention. CON will be virtually delivered by a study team member who will receive training and oversight from [name], who has delivered this intervention previously. In addition to class sessions, participants will be completed daily, 15-minute activities related to the course content (i.e. – designing a meal plan and grocery shopping list; creating a list of healthful take-out or restaurant meals; etc) at home. Time-in-treatment will be matched between conditions.

POST-INTERVENTION TESTING: Repeat baseline testing at the end of 8 weeks and at 6 months.

OPTIONAL POST-INTERVENTION TESTING AT 1 YEAR: 6 months after the post-intervention testing time point participants will be contacted and asked to complete follow-up questionnaires. These questionnaires are designed to assess participants' perceptions of the intervention and if they achieved their weight-loss maintenance goals.

STOPPING PROCEDURES and ADVERSE EVENTS: Participants will be encouraged to report any adverse events that they believe may have been a result of the study.

Procedures performed for research purposes only:

Statistical Methods, Data Analysis and Interpretation

The statistical analysis plan presented below was developed in collaboration with [name] of the SDBC.

Aim 1 will focus on the efficacy of the intervention (MORE vs. CON) on the primary outcome of body mass and body composition at week 8 and week 24. We will first provide descriptive summaries of each variable measured at week 0 (baseline), week 8 and 24, as well as by intervention group. Linear mixed models (LMM) will then be used to relate weekly assessments of body mass from week 0 to week 24 to the intervention, controlling for covariates likely to be associated with the outcome. Specifically, this will include baseline body mass and composition, and other demographic covariates including (but not be limited to) age, sex, race and socioeconomic status. Different slopes for time trend and intervention-time interaction term will be assumed for the intervention period (week 0-8) and follow-up period (week 8-24). Random intercepts will be used to account for correlations on the participant level. An advantage of this approach is treatment effect estimates remain consistent and approximately unbiased if missing data follow a missing-at-random pattern (MAR; data values are independent of missingness mechanism conditional on the observed data), the most general data-centric missing data assumption. Secondary analyses will fit separate LMM models to assess changes in fat mass and lean mass measured at week 0, 8 and 24. Similarly, LMM will be fitted for each of the eating behaviors and energy intake outcome collected for **Aim 2** (detailed above), where skewed outcomes may be transformed to approximate normality. Bonferroni correction will be performed to adjust for multiple comparisons.

Sample size, and power consideration: For a total of 100 participants randomized 1:1 to each study arm, we conservatively anticipate 20% attrition. This leaves us with complete data on n=80 participants total (n=40 per group). This provides $\geq 80\%$ power for detecting differences in body mass (or other outcomes assessed in Aim 1 and 2) by at least 0.89 standard deviations. We expect power will be greater for our primary analysis models when adjusting for covariates associated with outcomes. Although we will have limited statistical power for the current analysis this trial will generate the effect size necessary to power a future trial, while allowing us to collect outcome measures on a practical amount of participants within the 2-year award period.

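### Participants are taught in classes nested within arm, but the planned mixed model has no class term, so the MORE v CON standard error is too small if classmates' change is correlated beyond what concurrent classes in the other arm share

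*Combined protocol and SAP*

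**What the plan says.** In the protocol's Study Procedures, individuals are randomised 1:1 in blocks within sex. The INTERVENTION part then places both arms under the heading "Group-Based Interventions". For MORE the format is explicit: "MORE is delivered in a group format, consisting of 8 weekly HIPPA compliant virtual zoom 2-hour sessions". The CON paragraph does not use the word group, but it says "In addition to class sessions, participants will be completed daily, 15-minute activities related to the course content", which also implies classes. On who teaches, the text for MORE reads "The intervention will be delivered by a study team member who will receive training and supervision from" a named person, and for CON "CON will be virtually delivered by a study team member who will receive training and oversight from" a named person. It does not say whether one facilitator takes all classes in an arm.

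Under Statistical Methods, Data Analysis and Interpretation, the Aim 1 model is described as follows: "Linear mixed models (LMM) will then be used to relate weekly assessments of body mass from week 0 to week 24 to the intervention". Time trends differ between weeks 0-8 and 8-24. The only correlation structure given is "Random intercepts will be used to account for correlations on the participant level". The same type of model is used for fat mass, lean mass and each Aim 2 outcome. The sample-size section counts 40 completers per arm as independent and claims at least 80% "power for detecting differences in body mass (or other outcomes assessed in Aim 1 and 2) by at least 0.89 standard deviations". Class, cohort, wave, facilitator and design effect are not mentioned in either section.

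**The concern.** People who meet weekly for eight weeks with the same classmates and facilitator may come to change alike. Each class belongs to one arm, so variation between classes enters the arm contrast directly. A participant intercept cannot carry it, because it describes a person's overall level and not change shared with classmates. The covariate list is open-ended, but class cannot be added as an ordinary fixed covariate alongside arm, because it is nested in arm.

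At stake are the width of the intervals and the error rate of the tests, for Aim 1 and every Aim 2 outcome. The planned Bonferroni correction does not help, since it adjusts the threshold and leaves the standard error as it is. The sample-size section says the trial is meant to supply an effect size for powering a later trial. That estimate would come with an interval that is too narrow and with no class ICC.

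**Working it through.** **Inputs from the documents.** Individual 1:1 randomisation; 40 completers per arm after 20% attrition; participant intercepts only.

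**Assumptions, because the documents are silent.** Two-sided alpha 5%; closed classes of m = 5, 8 or 10 completers (k = 8, 5 or 4 classes per arm); ICC of change from 0 to 0.10.

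**1. The plan's own figure.** With 40 independent participants per arm, the difference detectable with 80% power is (1.960 + 0.842) × √(2/40) = 0.63 SD. Power at 0.89 SD is Φ(0.89/0.2236 − 1.960) = 97.8%. So 0.89 SD is not the 80% point at this sample size. That is a separate matter, and 0.63 SD is the reference used below.

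**2. Class-blind comparison of change, both arms clustered, class effects independent between arms.** The design effect is D = 1 + (m − 1) × ICC, and the actual type I error is 2 × [1 − Φ(1.96/√D)]. For m = 10 and ICC 0.05, D = 1.45, the true standard error is √1.45 = 1.20 times the one reported, and the error rate is 10.4%. Simulation (60,000 runs per cell) gives:

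| ICC | m = 5 | m = 8 | m = 10 |
|---|---|---|---|
| 0 | 4.9-5.0% | 4.9-5.0% | 4.9-5.0% |
| 0.01 | 5.6% | 5.7% | 6.0% |
| 0.02 | 6.0% | 6.6% | 7.1% |
| 0.05 | 7.3% | 9.1% | 10.4% |
| 0.10 | 9.8% | 13.5% | 15.9% |

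A t-test on class means stays at 4.8-5.1% throughout. If only MORE is clustered, the class-blind rates are 5.2-5.5% at ICC 0.01, 5.5-6.1% at 0.02, 6.3-7.5% at 0.05 and 7.5-10.4% at 0.10.

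**3. Does a participant intercept absorb the class effect?** This was simulated with data at weeks 0, 8 and 24, four classes of 10 per arm, and no other variation in individual change. Model standard error against the true SD of the estimate was 0.223 v 0.225 at ICC 0, 0.220 v 0.268 at 0.05 and 0.218 v 0.308 at 0.10. Type I error was 5.3%, 10.7% and 16.8%. The intercept does not absorb it. This layout matches the fat-mass and lean-mass models, not the weekly body-mass model.

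**4. Correlation shared between arms.** Suppose MORE and CON classes run in paired waves and a fraction s of the class variance is common to both members of a pair. The common part cancels in the contrast, and D becomes 1 − ICC + m(1 − s) × ICC. For five pairs of classes of 8 at ICC 0.05:

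- s = 0: D = 0.95 + 0.40 = 1.35, error 9.2% (simulated 9.3%)
- s = 0.5: D = 0.95 + 0.20 = 1.15, error 6.8% (simulated 6.9%)
- s = 1: D = 0.95, error 4.4% (simulated 4.4-4.6%)

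With s = 1, an unpaired class-mean test falls to 2.5-2.7%, while a paired one holds 5.0%.

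**5. Price of a class-level test.** The variance of the arm difference is (2/k)[ICC + (1 − ICC)/m], on 2k − 2 degrees of freedom (noncentral t, 80% power). At ICC 0.05 with k = 8 this is 0.25 × (0.05 + 0.19) = 0.060. The detectable differences at ICC 0.05 are 0.74, 0.83 and 0.91 SD for 8, 5 and 4 classes per arm, against 0.63 SD for 40 v 40 independent participants. Over ICC 0 to 0.10 the ranges are 0.67-0.80, 0.72-0.93 and 0.75-1.04 SD.

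**The case against.** Four points on the other side deserve weight.

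- **Everything that sets the size is assumed.** No document supports an ICC of 0.05 or 0.10, and at 0.01-0.02 with only MORE clustered the excess is about a percentage point or less. This stands, and it is why the conclusion is conditional. It does not remove the omission, since the plan offers no way to learn what the ICC was.
- **Positive correlation among classmates is not enough by itself.** If it came wholly from calendar time shared by concurrent MORE and CON classes, it would cancel (step 4). This stands, and the condition is worded accordingly. Class scheduling is not described, so neither case can be ruled out.
- **The percentages are not for the planned primary analysis.** This also stands. They describe a test on change, and a reader might infer that the weekly body-mass model has a type I error of 7-16%. The documents do not support that. The weekly model also lacks participant-specific slopes, which can distort its error rate with no class effect at all. That is a separate point and adds no weight to this one.
- **The efficacy comparison is called preliminary and power is conceded to be limited.** This limits the consequences. It does not excuse intervals that are too narrow around an estimate intended for planning.

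A reader might also infer that the effect estimate is biased, or that CON was certainly taught in groups. Omitting the class term affects the standard error, not the estimate, and the CON format rests on a heading and one phrase.

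**Conclusion.** The concern holds in conditional form. Group teaching after individual randomisation is explicit for MORE and a reasonable inference for CON, and the plan accounts for correlation within participants only. If classmates' change is correlated beyond what concurrent classes in the other arm share, the standard error of MORE v CON is too small and type I error exceeds nominal.

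Over the assumed range the excess runs from under one percentage point (ICC 0.01, small classes) to about 11 points (ICC 0.10, classes of 10), for a test on change at two-sided 5%. It is about nil at ICC 0 or with fully shared correlation. The analysis plan should be changed, with medium confidence in the practical size.

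**What to change.** - **Data.** Record class ID and class start date (wave) for each participant where they can be recovered, and state how participants with unknown class are handled.
- **Model.** Start from a model that already allows participants to differ in change, for example baseline-adjusted change at weeks 8 and 24. Add class nested in arm as a random effect on change, with Kenward-Roger or Satterthwaite degrees of freedom. If CON was not taught in groups, put the class term in MORE only. If MORE and CON classes ran in concurrent waves, include wave.
- **Sensitivity analysis.** Prespecify a class-mean comparison of change, paired by wave if classes were concurrent and unpaired otherwise. Report it whatever the estimated class variance.
- **Reporting.** Give the class ICC with its interval and call it imprecise. State the detectable difference over a range of class sizes and ICCs, and do not use 0.89 SD as the yardstick. If each arm had one facilitator, say that a class term cannot separate facilitator from arm.

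**Cost.** Two variables and some analysis wording; treatment and visits do not change. The work is partly retrospective, because the Informed Consent section has enrolment over as of March 2023 and nothing says whether class membership was kept. Intervals widen and degrees of freedom are few, as step 5 of the working shows. The class variance will often be estimated as zero: in simulations of the baseline-adjusted model without a wave term, this happened in 54-58% of runs at a true ICC of 0 and in 32-33% at 0.05. That model's type I error was 2.8-5.3% over ICC 0-0.10, conservative near ICC 0.

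### The only adverse-event provision described asks participants to volunteer events they themselves link to the study, so harms are likely to be under-counted

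*Combined protocol and SAP*

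**What the plan says.** Under Stopping Procedures and Adverse Events, the protocol gives one sentence: "Participants will be encouraged to report any adverse events that they believe may have been a result of the study". Nothing else in the documents deals with how adverse events are collected, classified or reported.

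The scheduled contacts at which events could be asked about are described without any such enquiry:

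- Post-intervention testing reads "Repeat baseline testing at the end of 8 weeks and at 6 months". The Baseline Testing list covers body measurements, eating-related questionnaires, dietary recall and the meal test.
- The optional 1-year contact consists of questionnaires: "These questionnaires are designed to assess participants' perceptions of the intervention and if they achieved their weight-loss maintenance goals".
- The instruments for eating-disorder risk, depression and alcohol use appear under Screening, ahead of the baseline list. The protocol does not say that they are repeated.

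On the arms, the Randomization paragraph states "Participants will be randomized 1:1 to MORE or CON". One arm is a mindfulness course ("MORE is delivered in a group format, consisting of 8 weekly HIPPA compliant virtual zoom 2-hour sessions"). The other is a lifestyle course ("Participants randomized to the control intervention will complete an 8-week healthful lifestyle program via HIPPA compliant zoom sessions"). Blinding is not mentioned. The Statistical Methods section contains no summary or analysis of harms.

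**The concern.** The sentence puts two filters in front of the safety record. The participant must suspect that the study caused the event, and must then come forward unprompted. Whether a health problem is related to an intervention is normally decided after the event has been recorded. Here the judgement is made beforehand, by the person least placed to see a pattern across participants.

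Any event that a participant puts down to something else is not solicited. This sample offers ready alternative explanations: some participants have had bariatric surgery and others are on weight-loss medication. A new problem may be credited to the operation or the drug and never mentioned.

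Two things are at stake. A later statement that few or no harms were seen would be weak evidence, because a low count could reflect the method of collection. And if readers compare the arms, the comparison rests on how readily participants in each programme blame the programme. The sample-size section says the trial is meant to inform a larger one, which would inherit this safety record.

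**Working it through.** The documents give no adverse-event rate, safety endpoint or safety sample size, so there is no figure of the plan's own to reproduce. The calculation below shows how a filter of this kind behaves. It does not estimate what will happen in this trial.

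**Inputs**

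- Number per arm: 50. The sample-size section says "For a total of 100 participants randomized 1:1 to each study arm, we conservatively anticipate 20% attrition", and 100 / 2 = 50.
- True risk that a participant has an event: p. Assumed to be 10%.
- Share of events that the participant both attributes to the study and reports: q. Assumed to be 1, 0.5 or 0.3.

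**Under-counting, with the same q in both arms**

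Expected reports per arm = 50 × p × q. Chance of no report in an arm = (1 − p × q)^50.

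| q | Expected reports per arm | Chance of no report |
|---|---|---|
| 1 | 50 × 0.10 × 1 = 5 | 0.90^50 = 0.005 |
| 0.5 | 50 × 0.10 × 0.5 = 2.5 | 0.95^50 = 0.077 |
| 0.3 | 50 × 0.10 × 0.3 = 1.5 | 0.97^50 = 0.218 |

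Some under-count follows whenever q is below 1. The proportion lost is 1 − q whatever the true risk. At q = 0.5, for example, assumed risks of 10%, 20% and 30% give 2.5, 5 and 7.5 reports against 5, 10 and 15 true events.

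**Comparison of arms**

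Observed ratio = true ratio × (q in MORE / q in CON).

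- Equal shares, such as 0.5 and 0.5: the ratio is unchanged. With equal true risks it stays at 1.0.
- Shares of 0.6 in MORE and 0.3 in CON, with equal true risk of 10%: 50 × 0.10 × 0.6 = 3 reports against 50 × 0.10 × 0.3 = 1.5, a ratio of 2.0.
- The same shares reversed: 1.5 against 3, a ratio of 0.5.

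A false difference between arms therefore needs unequal shares. The documents fix neither the direction nor the size of any inequality.

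**The case against.** The strongest reply is that the sentence is less restrictive than it may look. It encourages reporting and sets a low bar, since a possible link is enough. It does not say that events noticed by staff, or volunteered for other reasons, would be discarded. The consent pages are not among the material available, so what participants are told about reporting cannot be seen. All of this stands. A reader might infer that nobody will ever ask about events, or that unattributed events are barred from the record. The documents support neither; they support only the statement that no enquiry is described and that unattributed events are not solicited.

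A reader might also infer that the two arms will be filtered differently. That is not shown. Both are 8-week Zoom programmes with 15-minute daily home tasks, and contact time is matched. Participants will know the content of their own programme, but the documents do not say whether they are told which one is expected to do better. A difference in attribution is possible and no more. The no-report calculation uses the same share in both arms and so says nothing about it.

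Nor should the surgical patients be called recent. The inclusion criteria require 12 to 20 months since the operation, and the exclusions remove those with complications needing recent inpatient care. Medical weight-loss patients must have been stable on their drugs for three months, and active psychiatric problems are excluded. These criteria lower the expected event rate, but they do not provide a way of finding events that do occur.

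Finally, the plan has no safety objective and promises no comparison of harms between arms. That limits the consequence. It does not make the capture rule a sound one for whatever is eventually said about harms.

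**Conclusion.** The point holds as a weakness in how harms are ascertained. Followed as written, the rule solicits only events that participants connect with the study, and nothing else in the documents fills the gap. Under-counting is the expected direction. Its size is unknown: the 0.5%, 7.7% and 22% chances of an empty record in an arm depend on an assumed 10% risk and assumed reporting shares of 1, 0.5 and 0.3.

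Bias between the arms is a possibility to guard against and has not been demonstrated. The efficacy analyses, the sample size and the significance level are untouched, because adverse events are not an outcome in the analysis plan.

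**What to change.** Replace the sentence with a provision along these lines:

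- At the week 8 and 6-month contacts, and at 1 year for those who take part, ask every participant in both arms the same open question about any new or worsened health problem since the last contact, whether or not they think it is connected with the study.
- Collect the answer privately through REDCap. The group Zoom sessions are a poor setting for individual health questions.
- Keep spontaneous reporting open throughout, alongside the scheduled question.
- Record every event regardless of believed cause, and have the study team record relatedness as a separate item.
- Tabulate events by arm. Show all events as well as those judged related, because study team members also deliver the programmes and their judgement may not be blind to arm.

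The Informed Consent section places the end of enrolment at March 2023, so some contacts may already have passed. For those, say how events were captured whenever harms are reported, and add the question at the contacts that remain.

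The cost is one short REDCap item, at most 100 × 2 = 200 responses before any at 1 year, and one table. The real burden is that more unrelated events will have to be logged and reviewed. The question will not reach participants who drop out before a contact, and recall between contacts will be imperfect, so it reduces the under-count without removing it.
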